15. ASSESSMENTS OF SAFETY

15.1. Adverse Events and Serious Adverse Events

15.1.1. Definition of Adverse Events

15.1.1.1. Adverse Event

An AE is defined as any untoward medical occurrence associated with the use of the investigational product in humans, whether or not considered related to investigational product. An AE (also referred to as an adverse experience) can be any unfavorable and unintended sign (eg, an abnormal laboratory finding), symptom, or disease temporally associated with any use of the investigational product, without any judgment about causality and irrespective of route of administration, formulation, or dose, including an overdose.

AEs include, but are not limited to: (1) a worsening or change in nature, severity, or frequency of condition(s) present at the start of the study; (2) subject deterioration due to primary illness; (3) intercurrent illness; and (4) drug interaction. For reporting purposes, pregnancy is not considered an AE.

Subjects should be questioned in a general way, without leading the subject or asking about the occurrence of any specific symptom.

The Investigator should attempt to establish a diagnosis of the event based on signs, symptoms, and/or other clinical information. The diagnosis and not the individual signs/symptoms should be documented as the AE. For example, if the underlying disease process is a stroke, it would not be appropriate to record the AE by describing the symptoms “sudden numbness, dizziness, and difficulty speaking.” The AE medical term of “stroke or cerebrovascular accident” should be recorded as it more accurately describes the AE.

Subjects should be instructed to contact the site promptly if they develop any of the signs and symptoms of intercurrent illness and/or potential adverse events listed in [Appendix C](#).

15.1.1.2. Treatment-Emergent Adverse Event

A treatment-emergent AE (TEAE) is any event not present before the initiation of the investigational product or any event already present that worsens in either intensity or frequency following exposure to the investigational product.

15.1.1.3. Serious Adverse Event

An AE is considered “serious” if, in the view of either the Investigator or Sponsor, it results in any of the following outcomes:

- Death
- Is life threatening
- Requires in-subject hospitalization or prolongation of existing hospitalization
- Results in persistent or significant disability or incapacity
- Results in a congenital abnormality or birth defect

- Is an important medical event that may jeopardize the subject or may require medical intervention to prevent one of the outcomes listed above

Events **not** considered to be SAEs are hospitalizations for:

- Routine monitoring of the studied indication and not associated with any deterioration in condition or AE
- Elective treatment for a pre-existing condition that did not worsen
- Respite care or observation when there is no AE associated with the hospitalization

A PK blood sample should be collected in subjects who experience a SAE during the study. Blood samples should be collected as soon as possible after the SAE is identified but no later than 7 days after the onset of the SAE. The times of the last dose of investigational product, the last meal, and the PK sample collection will be recorded in the eCRF. If a PK sample cannot be collected within 7 days, the reason should be recorded in the eCRF.

15.1.2. Suspected Unexpected Serious Adverse Reaction

A SUSAR is defined as a suspected adverse reaction that is assessed as serious, causally related to the investigational medicinal product, and unexpected per the reference safety information (RSI) in the Investigator's Brochure.

SUSARs are subject to expedited reporting. The Sponsor shall ensure that all relevant information about SUSARs that are fatal or life-threatening are recorded and reported as soon as possible to the relevant competent authorities (either directly or through the Eudravigilance Clinical Trials Module, as applicable), and to the Ethics Committees, no later than 7 days after knowledge by the Sponsor of such a case. Relevant follow-up information is subsequently communicated within an additional 8 days. All other SUSARs shall be reported to the competent authorities concerned (either directly or through the Eudravigilance Clinical Trials Module) and to the Ethics Committees concerned, within a maximum of 15 days of first knowledge by the Sponsor. Each competent authority shall ensure that all SUSARs to an investigational medicinal product that are brought to its attention are recorded. The Sponsor shall also inform all participating Investigators, as applicable to the local regulations.

15.1.3. Relationship to Investigational Product

The Investigator will document her/his opinion of the relationship of the AE to treatment with the investigational product using the criteria outlined in [Table 8](#). An AE for which there is a "reasonable possibility" that the investigational product caused the AE is otherwise referred to as suspected adverse reaction (SAR). "Reasonable possibility" means there is evidence to suggest a causal relationship between the investigational product and the AE.

If the relationship between the AE/SAE and the investigational product is determined to be "definite," "possible" or "probable," the event will be considered to be related to the investigational product for the purposes of expedited regulatory reporting.

Table 8: Relationship of Adverse Events to Investigational Product

Relationship	Description
Definite	A reaction that follows a reasonable temporal sequence from administration of the investigational product or in which the investigational product level has been established in body fluids or tissue; that follows a known or expected response pattern to the suspected investigational product; and that is confirmed by improvement on stopping or reducing the dosage of the investigational product, and reappearance of the reaction on repeated exposure.
Probable	A reaction that follows a reasonable temporal sequence from administration of the investigational product; that follows a known or expected response pattern to the suspected investigational product; that is confirmed by stopping or reducing the dosage of the investigational product; and that could not be reasonably explained by the known characteristics of the subject's clinical state.
Possible	A reaction that follows a reasonable temporal sequence from administration of the investigational product; that follows a known or expected response pattern to the suspected investigational product; but that could readily be produced by a number of other factors.
Unlikely	An event that does not follow a reasonable temporal sequence from administration of the investigational product; that does not follow a known or suspected response pattern to the suspected investigational product; and that could reasonably be explained by known characteristics of the subject's clinical state.
Not Related	Any event that does not meet the above criteria.

15.1.4. Relationship to Liver Biopsy

The Investigator will document her/his opinion of the relationship of the AE to liver biopsy using the criteria outlined in [Table 9](#).

Table 9: Relationship of Adverse Events to Liver Biopsy

Relationship	Description
Related	A reaction that follows a reasonable temporal sequence from the liver biopsy; that follows a known or expected response pattern to the liver biopsy.
Not Related	Any event that does not meet the above criteria.

15.1.5. Recording Adverse Event Severity

AEs must be graded for severity (ie, intensity) using the current version of the CTCAE ([Appendix D](#)). A severity category of mild, moderate, severe, life threatening, or death as defined in [Table 10](#), must be entered on the AE CRF. Because a grading (severity) scale is provided for each AE term and not all grades are appropriate for all AEs, it may be necessary to refer to [Appendix D](#) before grading the severity of an event. It should be noted that the term "severe" used to grade intensity is not synonymous with the term "serious." The assessment of severity is made regardless of investigational product relationship or of the seriousness of the AE. When reporting AEs, reference should be made to the current version of the CTCAE manual for guidance on appropriate grading.

Table 10: Severity of Adverse Events

Grade	Clinical Description of Severity
1 = Mild	Asymptomatic or mild symptoms, clinical or diagnostic observations only, or intervention not indicated.
2 = Moderate	Minimal, local or noninvasive intervention indicated; or limiting age-appropriate instrumental activities of daily living ^a
3 = Severe	Medically significant but not immediately life-threatening, hospitalization or prolongation of hospitalization indicated, disabling, or limiting self-care activities of daily living. ^b
4 = Life-threatening	Urgent intervention indicated.
5 = Death	Death related to AE.

^a Instrumental activities of daily living refer to preparing meals, shopping for groceries or clothes, using the telephone, managing money, etc.

^b Self-care activities of daily living refer to bathing, dressing and undressing, feeding self, using the toilet, taking medications, and not bedridden.

15.1.5.1. Severity of Pruritus (as an AE)

To ensure consistency in reporting, pruritus AEs must be graded for severity (ie, intensity) using the current version of the CTCAE ([Appendix D](#)) the category definitions are included in [Table 11](#) for reference. As pruritus is a subjective symptom, clinical judgment should be used to determine its management.

Table 11: Severity of Pruritus

Pruritus Grade	Clinical Description of Severity for Pruritus
1 = Mild	Mild or localized; topical intervention indicated.
2 = Moderate	Intense or widespread; intermittent; skin changes from scratching (eg, edema, papulation, excoriations, lichenification, oozing/crusts); oral intervention indicated; limiting instrumental activities of daily living.
3 = Severe	Intense or widespread; constant; limiting self-care activities of daily living or sleep; oral corticosteroid or immunosuppressive therapy indicated.

Since pruritus is a subjective symptom, the occurrence and magnitude of which are not readily measured objectively, clinical judgment needs to be applied in the management of each subject. Managing OCA-related pruritus may help improve tolerance in those subjects who experience problematic pruritus and may otherwise discontinue from the study prematurely. Guidance for the management of subjects experiencing significant pruritus are provided in [Table 4](#) ([Section 7.7](#)) and includes:

- Pruritus \geq Grade 3 in severity: Discontinue investigational product
- Pruritus \leq Grade 2 in severity: One or more of the following may be considered:
 - Drug holiday or less frequent dosing at the discretion of the Investigator.
 - Short-term use of BAS

- Use of BAS may be considered in conjunction with a change in investigational product dosing frequency (ie, every other day dosing) for approximately 2 weeks. The subject should be evaluated after the 2-week intervention to assess the status of pruritus and stop the use of BAS as deemed appropriate by the Investigator. If the Investigator considers that the subject can tolerate investigational product, daily dosing may be reinitiated.
 - If the subject cannot tolerate investigational product after stopping BAS due to ongoing pruritus, the Investigator should consult with the Medical Monitor to determine a treatment plan. This may include continuing every other day dosing, interrupting, or discontinuing investigational product.
 - If after 4 to 6 weeks (or up to 3 courses of a 2-week BAS therapy), the subject is unable to tolerate investigational product without BAS treatment, the Investigator should consider, in consultation with the Medical Monitor, discontinuing investigational product.
 - The subject should make every effort to avoid long-term use of BAS for pruritus while taking investigational product. For additional guidance on BAS refer to [Section 9.3](#).
- Other medical therapies may be considered, as deemed clinically appropriate and based on current practice guidelines ([EASL 2017](#)) or literature ([Hegade 2015](#)).

15.1.6. Reporting of Adverse Events and Serious Adverse Events

15.1.6.1. Reporting of Adverse Events

AE data will be collected from the time that signed informed consent is obtained until the subject fully completes her/his study participation of the study.

All AEs, whether believed by the Investigator to be related or unrelated to the investigational product, must be documented in the subject's medical records, in accordance with the Investigator's normal clinical practice and on the AE CRF. Each AE is to be evaluated for duration, intensity, frequency, seriousness, outcome, other actions taken, and relationship to the investigational product. Redacted medical record source documentation will be requested for all SAEs and emergency room visits.

[figure not shown]
In addition, the Investigator should contact the study Medical Monitor promptly when any signs or symptoms of hepatic decompensation are observed in any subject.

15.1.6.2. Reporting of Serious Adverse Events

In agreeing to the provisions of this protocol, the Investigator accepts all legal responsibilities for immediate reporting of SAEs to the Sponsor. Immediate reporting implies within 24 hours of becoming aware of the occurrence of an SAE.

All SAEs must be reported to the Sponsor (including potential liver-related clinical outcome events that qualify as serious).

SAEs are reported by entering the SAE data into the study specific EDC system. Entering the SAE data into the EDC system will automatically notify the Sponsor of the event. In the event that the EDC system is inaccessible, an SAE may be reported by:

If an SAE is reported by fax, an SAE Report form must also be completed in the EDC system as soon as the EDC system is accessible. At a minimum, the following information should be provided at the time of the initial report:

- Subject number
- Event term
- At least 1 criterion classifying the event as serious
- Name and title of the reporting individual
- Causal relationship to the investigational product

The Investigator will assess whether the event is causally related to the investigational product. The Sponsor will also assess whether the event is causally related to the investigational product, in addition to assessing the overall safety profile of the investigational product. The Sponsor will notify the appropriate regulatory agencies as well as all participating Investigators of investigational new drug (IND) Safety Reports/Expedited Safety Reports that occur during the study within the time frames required by each regulatory agency.

Following the initial report, any additional information obtained by the Investigator about the SAE must be reported promptly to the Sponsor in the same manner as described above for the initial SAE report. Any supporting source documentation should be faxed to [REDACTED] or emailed to [REDACTED] as soon as possible.

The Investigator is responsible for submitting information on IND Safety Reports/Expedited Safety Reports received from the Sponsor to her/his local IRB/IEC, as directed by the local-country requirements. Documentation of the submissions to IECs/IRBs must be retained in the appropriate study file(s). As instructed by the Sponsor, IND Safety Reports/Expedited Safety Reports should be retained in the appropriate investigative site study files, or with the IB.

SAEs involving potential liver-related clinical outcome events will be processed and reported by the Sponsor as described in [Section 15.1.7](#).

15.1.7. Potential Liver-Related Clinical Outcome Events

Specified liver-related clinical outcome events may, by definition (see [Section 15.1.1.3](#)) qualify as SAEs. The Sponsor must be notified of any SAEs within 24 hours of the site becoming aware of the event (see [Section 15.1.6.2](#)). The Sponsor is responsible for regulatory reporting of SAEs, including expeditious reporting of SUSARs, refer to [Section 15.1.2](#) for definition of SUSAR.

Given that the liver-related clinical outcome events could also meet the criteria of a SUSAR, which would necessitate unblinding for expedited reporting, the Sponsor will not expeditiously report potential liver-related clinical outcome events in order to retain the study blind and preserve the integrity of the clinical outcomes endpoint. These events will be selected as a

“study event” on the Adverse Event CRF and will be submitted for adjudication to the Hepatic Outcomes Committee as described in [Section 16.11](#).

The Sponsor will consider the following list of clinical outcome events (MedDRA preferred terms) to be disease related and exempt from expeditious regulatory reporting, but will continue to report them in a non-expeditious manner: death, end-stage liver disease (preferred term: chronic hepatic failure), liver transplant (preferred term: liver transplant), [REDACTED], [REDACTED], variceal bleeding (preferred terms: gastroesophageal variceal haemorrhage, esophageal varices haemorrhage), hepatic encephalopathy (preferred term: hepatic encephalopathy), spontaneous bacterial peritonitis (preferred term: peritonitis bacterial), ascites secondary to cirrhosis (preferred term: ascites), and progression to cirrhosis (preferred term: hepatic cirrhosis).

15.1.8. Additional Investigator Responsibilities for SAEs

The safety data recorded in the CRF represent the official record of all AEs and SAEs reported in the study. The Investigator should comply with requests by the Medical Monitor or other Sponsor personnel to record the SAE on the subject’s AE CRF. Other supporting documents such as radiology reports, hospital discharge summaries, and autopsy reports should also be provided, when appropriate. Additionally, upon request by the Sponsor, the Investigator should provide input into the SAE narrative and provide timely information to ensure prompt follow-up and closure of the SAE report.

The Investigator and supporting personnel responsible for subject care should discuss with the Medical Monitor any need for supplemental investigations of SAEs. The results of these additional assessments must be reported to the Medical Monitor.

15.1.9. Notification of Post-Treatment SAEs for Subjects Who Continue in the Study

Post-treatment SAEs that occur in subjects who remain in the study after investigational product has been discontinued must be reported to the Sponsor within 24 hours by following the instructions provided in [Section 15.1.6.2](#).

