7.7. Investigational Product Adjustment, Interruption, and Discontinuation Criteria

Dosages for investigational product should be maintained constant during the study. However, adjustments, interruptions, discontinuation, and any rechallenge of investigational product should be implemented per the criteria outlined in [Table 4](#).

Subjects can be temporarily or permanently discontinued from investigational product by the Investigator at any time for clinical safety concerns. If investigational product is temporarily or permanently discontinued, a PK sample must be collected within 7 days. If a PK sample cannot be collected within 7 days, the reason should be recorded in the eCRF.

- Subjects who are temporarily discontinued from investigational product are expected to continue in the study and should follow the regular visit schedule for the duration of the study. The Investigator should use their clinical judgement to determine if more frequent assessments of laboratory tests and symptoms are necessary.
- Subjects who permanently discontinue from investigational product are expected to continue in the study and should follow the regular visit schedule for the duration of the study. The Investigator should use their clinical judgement to determine if more frequent assessments of laboratory tests and symptoms are necessary until stabilization of the clinical event leading to discontinuation has occurred (per discretion of the Investigator and upon discussion with the medical monitor [[Section 7.4.3](#)]). The subjects will not be rechallenged with investigational product.

Subjects who interrupt treatment will be monitored to determine if or when investigational product may be restarted. However, an interruption of investigational product may result in treatment discontinuation. In this instance, an EOT or EOS visit should occur only after discussion of the event with the sponsor's medical monitor. The investigator should obtain a liver biopsy at the EOT visit to characterize any histological changes during the period that the subject was taking investigational product.

Prior to re-starting investigational product after a prolonged interruption, the subject must be re-consented and new baseline visit procedures must be performed if the interval from the last visit was more than 3 months (+2 weeks) during the first 18 months of the study or more than 6 months prior (+2 weeks) during the remainder of the study.

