^b Outcomes data to be discussed or collected include data related to adjudicated event-related data. No additional data (eg, AE, concomitant medication, etc.) data will be collected, except as indicated in Section 15.1.9.

Some assessments noted below may be omitted if they have been completed within 6 months (or the timeframe otherwise specified) and so long as safety issues do not warrant repeat testing.

EOS and/or EOT Visit procedures for all subjects are as follows:

- Verify that the subject has fasted for at least 8 hours
 - Record fasting status in the source and CRF

- If the subject reports having eaten within 8 hours, document accordingly in the source and CRF and remind the subject that fasting is required before all study visits after screening.
- Perform a physical examination
- Perform a standard 12-lead ECG
- [REDACTED] and vital signs (body temperature, sitting heart rate, respiratory rate, and sitting blood pressure)
- [REDACTED]
- Determine alcohol consumption (AUDIT questionnaire), smoking habits, and caffeine consumption
- Assess and record AEs
- Review and record concomitant medications
- [REDACTED]
- Perform hepatobiliary ultrasound for [REDACTED] and for gallbladder assessment (not required at EOT/EOS if done within 6 months of visit)
- Obtain liver biopsy (not required if biopsy has been done within 6 months of the EOT/EOS Visit)
- [REDACTED]
- Serum chemistry, hematology, and coagulation
- Thyroid hormones
- Free fatty acids
- Insulin, c-peptide, and HOMA-IR
- Glucose and HbA1c
- [REDACTED]
- Apoptosis markers (CK-18 M30 and CK-18 M65; only for subjects that discontinue investigational product before or on Month 18 visit)
- Noninvasive assessments of liver fibrosis: ELF, Fibrotest/Fibrosure
- Inflammation marker (hs-CRP)
- [REDACTED]

- Evaluate signs and symptoms of hepatic injury or decompensation and assess subjects per Suspected DILI Management and Progression to Cirrhosis Algorithms and intercurrent illness and/or potential adverse events ([Appendix C](#))
- Calculations will be performed by the Sponsor or designee for
 - MELD score
 - [REDACTED]
 - [REDACTED]
- Obtain urine sample for urinalysis
- Perform a urine-based β -hCG pregnancy test for females of childbearing potential
- Collect all used and unused bottles of investigational product, assess investigational product compliance, and perform investigational product accountability

EOS and/or EOT Visit procedures for the various subsets of subjects are as follows:

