16.9.1. Adverse Events

AEs will be coded using the Medical Dictionary of Regulatory Activities (MedDRA). Summary tables of treatment-emergent AEs will be provided. The incidence of TEAEs will be tabulated by system organ class and preferred term for each treatment group, and by severity and relationship to treatment. Summaries of TEAEs leading to investigational product discontinuation and SAEs will be provided.

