### 10.3. Adverse Events

AE data will be collected from the time that signed informed consent is obtained until the subject fully completes her/his study participation of the study. AEs will be reported and categorized using the Common Terminology Criteria for Adverse Events (CTCAE, Version 4.03).

All AE summaries will be restricted to TEAEs, which are defined as any AEs that newly appear, increase in frequency, or worsen in severity following randomization up to 30 days from the last dose date of permanent investigational product discontinuation up to new data cut-off date. If it cannot be determined whether the AE is treatment emergent due to a partial onset date, then it will be counted as such. Verbatim terms on eCRFs will be mapped to preferred terms (PT) and system organ classes (SOC) using MedDRA version 18.1 or later version.

Each AE summary will be displayed by treatment group. Summaries that are displayed by SOC and PT will be ordered by descending order of incidence (OCA 25 mg, followed by OCA 10 mg, followed by placebo) of system organ class and preferred term within each system organ class. Summaries of the following types will be presented:

- Overall summary of TEAEs
- Subject incidence of TEAEs and the total number of entries by MedDRA SOC and PT.
- Subject incidence of TEAEs and the total number of entries by PT in descending order.
- Subject incidence of serious TEAEs and the total number of entries by MedDRA SOC and PT.
- Subject incidence of TEAEs leading to investigational product withdrawal by MedDRA SOC and PT.
- Subject incidence of TEAEs leading to study discontinuation by MedDRA SOC and PT.
- Subject incidence of TEAEs by MedDRA SOC, PT, and highest severity (CTCAE grade). At each level of subject summarization, a subject is classified according to the highest severity if the subject reported 1 or more events. AEs with missing severity (CTCAE grade) will be considered grade 3 (severe) for this summary.
- Subject incidence and total number of entries of CTCAE grade 3 or higher TEAEs by MedDRA SOC and PT. At each level of subject summarization, a subject is

classified according to the highest severity if the subject reported 1 or more events. AEs with missing severity (CTCAE grade) will be considered grade 3 (severe) for this summary.

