## 10.4. Adverse Events of Special Interest

The following treatment-emergent AESIs will be summarized:

- Pruritus
- Hepatic
- Cardiovascular
- Dyslipidemia
- Gallbladder disease and related complications
- Pancreatitis
- Renal
- Urolithiases
- Hyperglycaemia/New onset diabetes mellitus

Each subcategory of interest will be defined using Standardized MedDRA Queries (SMQs) and/or custom MedDRA queries, as specified in the subsequent sections.

AESI analyses will include all of the following:

- Incidence of treatment-emergent AESIs by PT
- Incidence of treatment-emergent AESIs by PT and severity
- Incidence of serious treatment-emergent AESIs by PT
- Incidence of treatment-emergent AESIs leading to IP withdrawal by PT
- Incidence of related treatment-emergent AESIs by PT
- Incidence of treatment-emergent AESIs leading to death by PT
- Exposure-adjusted incidence of AESIs by PT
- Exposure-adjusted incidence of serious AESIs by PT
- Exposure-adjusted incidence of AESIs by baseline diabetes status
- Exposure-adjusted incidence of severe (Grade 3+) AESIs by PT
- KM statistics and plot for time to first onset of treatment-emergent AESI
- KM statistics and plot for time to onset of first severe (Grade 3+) or serious treatment-emergent AESI
- KM statistics and plot for duration of first treatment-emergent AESI
- KM statistics and plot for duration of most severe treatment-emergent AESI
- Percentage of subject-days with treatment-emergent AESIs per subject exposure year (SEY), by severity

All summaries noted above will include crude incidence rates for each level of summation. For overall incidence summary of AESI, analyses will be performed separately for AESI collected on-treatment only and during study.

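### Serious adverse events are collected for as long as a subject stays in the study off drug, but the SAP's general serious and fatal AE tables stop 30 days after the last dose, with no on-study by-arm counterpart

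*Protocol*

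**What the plan says.** **Collection.** Protocol 15.1.9: "Post-treatment SAEs that occur in subjects who remain in the study after investigational product has been discontinued must be reported to the Sponsor". Protocol 15.1.6.1 collects AE data from consent "until the subject fully completes her/his study participation of the study". Protocol 7.7 adds: "Subjects who permanently discontinue from investigational product are expected to continue in the study". Subjects who move to telephone contact or record review (Protocol 9.9.9, Table 6, footnote b) give no further general AE or medication data, but serious events remain the exception: no additional "data will be collected, except as indicated in Section 15.1.9".

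**Definition and reporting in the protocol.** A TEAE is a new event or, in Protocol 15.1.1.2, "any event already present that worsens in either intensity or frequency following exposure to the investigational product". No end date is given. Protocol 16.9.1 states: "Summaries of TEAEs leading to investigational product discontinuation and SAEs will be provided". No window is attached.

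**Reporting in the SAP.** SAP 10.3: "All AE summaries will be restricted to TEAEs". It closes the TEAE window 30 days after the last dose at permanent discontinuation. The tables of serious, Grade 3 or higher and fatal events, and the serious-event listing, are all defined as subsets of TEAEs. SAP 10.4 makes one exception. For the overall AESI incidence summary, "analyses will be performed separately for AESI collected on-treatment only and during study". The serious and fatal AESI tables in the same section are labelled treatment-emergent.

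**The concern.** Long-term safety is an end-of-study objective in both documents (Protocol 6.7; SAP 2.1.2.4), and stoppers are followed for years, with a minimum of about 4 years in a study of about 10. The primary efficacy estimand counts events after drug discontinuation under a treatment policy strategy (SAP 2.3.2.1). General serious harm is not given the same reach.

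Two things are at stake. First, data that sites must report would enter no comparison by arm. Second, the general SAE tables show crude subject percentages. If one arm stops drug sooner, its subjects are watched for less time and its percentage falls for that reason alone. Stopping can be related to drug: Protocol Table 4 ties discontinuation to severe pruritus, pancreatitis and related Grade 3 or higher events. Protocol 5.3 reports pruritus discontinuations of 0, 0, 2 and 5 subjects at placebo, 10, 20 and 40 mg in an earlier study.

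**Working it through.** The plan states no figure for this point, so there is none to reproduce. The check is a comparison of the texts, followed by an illustration on assumed rates.

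**Where an event starting more than 30 days after permanent discontinuation would appear, by arm**

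| Event | By-arm analysis reaching off-drug time |
|---|---|
| Death, any cause | Yes: primary composite, its components, and time from randomization (SAP 6.4.4.2, 6.4.7.1, 10.4.9.1) |
| Hepatic clinical outcomes, HCC | Yes: censored at last contact (SAP 4); components and HCC in SAP 6.4.7.1 |
| Adjudicated CV events, CV death | Yes: timed from randomization (SAP 10.4.9.1); censored at last contact (Protocol 16.9.3) |
| Any AESI, overall incidence | Yes: during-study version (SAP 10.4) |
| Serious or fatal AESI | No: labelled treatment-emergent (SAP 10.4) |
| Other SAE, such as infection or non-liver malignancy | No |
| Non-CV cause of death | No fatal-AE table; the death itself is counted |

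The hepatic, dyslipidemia, renal and CV subsections of SAP 10.4 also list SAEs by preferred term without the words treatment-emergent. The blanket rule in SAP 10.3 appears to govern them.

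**Illustration: inputs.** From the documents: window w = 30/365.25 = 0.082 years; minimum follow-up about 4 years. Assumed, because the documents give none: constant stopping hazard d, constant first-SAE hazard s (equal between arms, on and off drug), and complete follow-up to T years.

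**Share of in-study time outside the window** = 1 − [w + (1 − exp(−d(T − w)))/d]/T.
For d = 0.05 and T = 6: 1 − [0.082 + (1 − 0.744)/0.05]/6 = 13%. For d = 0.10 and 0.15 it is 24% and 33%. At T = 4 the three values are 9%, 17% and 24%.

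**Probability that the first SAE falls in the window** = 1 − exp(−sw) + exp(−sw) · s/(s + d) · (1 − exp(−(s + d)(T − w))).
Take s = 0.08 and T = 6, so T − w = 5.918 and exp(−sw) = 0.9935.
- d = 0.06: 0.0065 + 0.9935 × 0.5714 × (1 − exp(−0.8285)) = 0.0065 + 0.3198 = 32.6%.
- d = 0.09: 0.0065 + 0.9935 × 0.4706 × (1 − exp(−1.0060)) = 0.0065 + 0.2966 = 30.3%.
- On-study, either arm: 1 − exp(−0.48) = 38.1%.

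The rule omits 14.4% of first SAEs at d = 0.06 (1 − 32.63/38.12) and 20.5% at d = 0.09 (1 − 30.31/38.12). The 2.3-point gap is spurious. Over s = 0.05 to 0.10 and T = 4 to 6, the same formula gives omissions of 9.9% to 14.9% and 14.4% to 21.1%, and gaps of 0.8 to 2.7 points.

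**Sensitivity to the stopping rates (s = 0.10, T = 6; 45.1% on-study)**

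| Assumed stopping per year | Tabulated | Ratio |
|---|---|---|
| 5% vs 10% | 39.7% vs 35.2% | 0.89 |
| 5% vs 15% | 39.7% vs 31.5% | 0.79 |
| 10% vs 10% | 35.2% vs 35.2% | 1.00 |

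Exchanging the arms reverses the direction. With a constant hazard, events divided by person-time to first event or cut-off equal s in both arms, so a person-year rate does not show this distortion.

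**The case against.** The strongest reply is that most of the gravest off-drug events are analysed by arm elsewhere, as the first table shows. The nine AESI categories cover the harms of known concern, and their overall incidence is run during study. That stands, and it confines the gap to the three rows marked No.

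Second, off-drug SAEs are not hidden. SAP 4 promises by-subject listings of CRF data, and the DMC reviews SAE narratives and a cumulative SAE list (Protocol 16.10). This also stands, but neither is a comparison by arm in the final report.

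Third, giving an open-ended protocol definition a window in the SAP is ordinary practice, and Protocol 16.9.1 does not expressly promise an off-drug SAE table. That is correct. The case rests on data collected and left out of comparison, not on a broken promise.

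Fourth, the exposure-adjusted rates in SAP 10.4 cut events and person-time at the same point and so avoid the crude bias. True, but they are planned for AESIs; the general tables in SAP 10.3 give crude subject incidence.

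Fifth, the illustration assumes complete off-drug follow-up and equal hazards on and off drug, while subjects may withdraw or be lost. That limits the figures to illustration. It does not affect the omission.

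**Conclusion.** The gap is real and moderate. SAEs, fatal events and serious AESIs that begin more than 30 days after permanent discontinuation have no by-arm SAE or fatal-AE table, although sites must report them. This follows from the text and needs no assumption.

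Three stronger readings are not supported:
- A reader might infer from the word All in SAP 10.3 that every AE summary stops at 30 days. The during-study AESI summary in SAP 10.4 contradicts this; the two sections need reconciling.
- A reader might infer that off-drug deaths and liver or cardiovascular outcomes go unanalysed. They are analysed by arm, with follow-up beyond the drug.
- A reader might infer that the 25 mg arm will lose more SAEs and look safer than it is. That needs more stopping on 25 mg and a similar SAE rate off drug. The documents give no stopping rates by arm, and with equal rates the ratio is 1.00.

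On the assumed 6% versus 9% stopping per year, with an equal SAE hazard of 5% to 10% per year over 4 to 6 years, the spurious difference in crude incidence is 0.8 to 2.7 percentage points.

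**What to change.** In SAP 10.3:
- Keep the TEAE tables as they are.
- Add, by arm and by SOC and PT, tables of SAEs and of fatal AEs from first dose to last contact. Include serious AESIs.
- Give rates per person-year to first event or last contact beside the percentages.
- Reword the restriction to TEAEs so that it agrees with the during-study AESI summary in SAP 10.4, and say whether the SAE summaries in the SAP 10.4 subsections are treatment-emergent or on-study.
- State the same TEAE window in Protocol 15.1.1.2 and SAP 10.3.

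Do not extend the on-study tables to non-serious or Grade 3 or higher AEs. Those data stop for subjects on telephone contact or record review, so such tables would be incomplete.

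The cost is a few tables from data already collected. The downside is that off-drug events dilute an on-drug signal; the retained TEAE tables still show that signal.
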